We will employ a SMART design (see diagram in Section C, page 8) to evaluate the effectiveness of New Hope (NH), Elders' Resilience intervention (ER), Case Management (CM) and the combination of these approaches on reducing suicidal thoughts and promoting resilience among AI youth ages 10-29 who are confirmed by surveillance case managers to have recently experienced suicide ideation, attempt or a binge substance use and ideation. Youth who assent will complete the baseline (case management visit 1 and will be referred to mental health care—the standard protocol for the Apache system). During the same visit, youth will be randomized 1:1 to either New Hope (NH) plus Case Management (CM), or CM alone, using a blocked randomized design, stratifying participants by age and event type. All youth will complete another study assessment after 30 days. The 30-day time frame will allow ample time to complete the NH intervention with participants and assess any changes in youth's mental health status for all study arms. Following another 30-day period, all participants will be re-assessed and re-randomized, using the same blocking and 1:1 ratio to either the Elders' Resilience (ER) intervention plus CM, or CM alone. To track long term outcomes, all youth will complete a final assessment 3 month later (6 months post-enrollment). This study will occur on the White Mountain Apache Tribe's Fort Apache reservation.

For the Opioid Data Collection Sub-Study, we will use the opioid use questions added to the SMART trial assessment battery (see Assessment Table and Appendix) as a screener for sub-study participation to identify those who are currently using opioids. If current or recent opioid use is identified, an additional qualitative interview (~60-90 mins; see Appendix for guide) among a subset of participants (n = 30). This interview will be recorded and transcribed. Note: The opioid questions are not a screener for the intervention study.

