Aim 1 & 3: Research Program Assistants will obtain permission from the youth's parent, legal guardian or other legal authority (if the child is in foster care) if the youth is under 18 years of age. The study will be explained to the parent by the Research Program Assistant, including the nature of the study, the reason the child is being asked to participate, and nature of data gathering. If the parent is interested in having their child participate in the study, a Research Program Assistant will ask the parent to complete the parental permission form and will ask if they may obtain assent from the youth.

h. If you are seeking a waiver of informed consent or assent, the justification for this request:

N/A

i. Whether you will include a witness to the consent process and why:

Aim 1 & 3: No witness is needed. Participants or their parents must speak English, be literate, and not visually impaired.

j. If the language is unwritten, explain how you will communicate accurate information to potential participants and whether you will use props or audio materials:

[figure not shown]
N/A

2. Identify the countries where the research will take place, and the languages that will be used for the consent process.

| Country | Consent Document(s) (Adult Consent, Parental Permission, Youth Assent, etc.) | Languages |
|--------------------------|------------------------------------------------------------------------------------|-----------|
| United States of America | Aim 1: Adult Consent | English |
| United States of America | Aim 1: Parental Permission | English |
| United States of America | Aim 1: Youth Assent | English |
| United States of America | Aim 3: Adult Consent | English |
| United States of America | Aim 3: Parental Permission | English |
| United States of America | Aim 3: Youth Assent | English |
| United States of America | Aim 3: Adult Consent (Roundtables) | English |

C. Study Implementation:

1. Describe the procedures that participants will undergo. If complex, insert a table below to help the reviewer navigate.

Aim 1: STUDY PROCEDURE (Fig. 5 Study Design)

Once participants are identified via the surveillance system and consent/assent is completed, Research Program Assistants will administer the **baseline assessment (CM1)**. During the same visit (**CM1**), participants will be stratified by gender and event type, and then randomized to New Hope (NH) plus CM, or CM alone.

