Randomization Procedure 1. Participants will be stratified by age groups (10-14, 15-19, and 20-29) and event type (ideation, attempt, binge + recent ideation), then randomized to the control or intervention condition using a 1:1 assignment ratio. Re-randomization of all participants will occur again at **CM3** (another 30 days or 60 days/2 months post-baseline assessment).

Control Condition: Monitoring and Case Management (CM): Research Program Assistants, who are trained Surveillance System Staff, will conduct the monitoring and case management visits in participants' homes or other private settings at baseline, 1, 2, 3 and 6 months post-enrollment. This time-period was selected as the highest risk period for a subsequent suicide event following an initial episode.[12, 13] The CM visit includes rapport-building, use of the Suicide Ideation Questionnaire (SIQ) to assess imminent risk, and if youth report not yet having connected to services, referral to Apache Behavioral Health Services (ABHS), the local community mental health center. As we have added opioid related questions through an administrative supplement, the monitoring and case management visits will also allow us to track any safety concerns related to opioids and provide appropriate referrals to treatment. If minors seek treatment elsewhere or express disinterest, case managers will also facilitate connections to other care providers

(traditional healers, church, IHS social services/mental health, and private providers). At CM visits, the **Research Program Assistants will also monitor participants' completion of the study battery**, which will be self-administered using tablets. In addition, Research Program Assistants will score the SIQ before leaving the youth. If the SIQ reveals the participant is at imminent risk, Research Program Assistants will employ a protocol for rescue services (*described below*), which involves triaging youth immediately to the ED for further assessment and care.

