All youth will complete another study assessment after 30 days (**CM2**). The 30-day time frame will allow ample time to complete the NH intervention with participants and assess any changes in youth's mental health status for all study arms. Following another 30-day period (**CM3**), all participants will be re-assessed and re-randomized, using the same blocking and 1:1 ratio to either the Elders' Resilience (ER) intervention plus CM, or CM alone.

Randomization Procedure 2. Participants will be stratified by age groups (10-14, 15-19, and 20-29) and event type (ideation, attempt, binge + recent ideation), then randomized to intervention condition using a 1:1 assignment ratio.

Intervention 2: Elders' Resiliency (ER) intervention. Our CAB, Elder's Council and other key stakeholders have taught us that Apache traditions confer behavioral repertoires and values taught through storytelling, observation, and parenting at the family and community level that have carried the Apache people through generations of adversity and historical trauma. Starting in 2015, CAIH and local suicide prevention staff helped Apache Elders to create and teach a monthly manualized curriculum intended to bolster Apache youths' resilience to suicide ideation, attempts and substance abuse by promoting Apache cultural identity and values, youth's self-worth and role in the community, and fostering connectedness to society and community, *with an emphasis on extended family as a nexus of strength*. Each lesson

introduces youth to cultural knowledge, stories, and songs with an emphasis on respect and the sacredness of each life. Specific themes include: respect, Apache culture, spirituality, self-worth, endurance, gender roles, Apache history, education/work, responsibilities, relationships (including the clan system), discipline and communication. The Elders, CAIH, and suicide prevention team are now adapting the monthly curriculum into a brief intervention for youth who come through the surveillance system. ER will be provided by a separate CMHW and an Elder to reduce potential bias in the assessments.

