Aim 3: The qualitative interview should take no longer than 45 minutes and will be done at a convenient time. There will only be one-two study visits, although stakeholders will be encouraged to provide feedback at any time about their experiences with the Southwest Hub's key intervention components. For the online survey, the survey is expected to take 20 minutes and will be administered twice a year in years 2-5, for a total of 8 time points. *The opioid roundtables are estimated to take 60-90 minutes.*

4. Provide a brief data analysis plan and a description of variables to be derived.

Primary and Secondary Outcomes

Aim 1: Given the longitudinal nature of the data, we will use mixed-effects regression models (MRMs)[41] to estimate average treatment effects while accounting for shared variance of repeated measures within adolescent. MRMs are highly flexible, addressing: variability in number and spacing of measurements, a variety of outcome distributions, linear and non-linear patterns of change (e.g., quadratic), and are robust to missing data.

Suicide ideation (primary outcome): Measured by the Suicide Ideation Questionnaire (SIQ/SIQ-JR). The SIQ is a 15-item scale that analyzes frequency and severity of suicidal ideation over the past 6 months. Items are scored on a 7-point scale ranging from 0 “I never had this thought” to 6 “Almost every day.” Scores of 30 for the SIQ and 23 for the SIQ-JR indicate severe suicidal ideation and need for clinical intervention. The scale has been used among AI adolescents with sound psychometric properties (Cronbach’s alpha=0.97).[22]

Resilience (secondary outcome): Measured by The Resiliency Scales. These are self-report scales measuring the individual’s Sense of Mastery (MAS; composed of 20 items), the Sense of Relatedness (REL; 24 items), and the Emotional Reactivity (REA; 20 items). Each item has five response choices ranging from 0 (Never) to 4 (Almost Always).

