| Voices of Indian Teens Cultural Issues and Interest | X | X | X | X | X | | |
| Rosenberg Self Esteem Scale | X | X | X | X | X | | |
| Index of local indicators of well-being | X | X | X | X | X | | |
| COVID-19 Questions | X | X | X | X | X | | |
| Exit Interview Questions | | | | | X | | |
| Opioid Data Collection Sub-Study: Opioid Follow-Up Interview (offered at first assessment point they endorse use) | X | X | X | X | X | | |
| JHU Acceptability | | | | | | | X |
| JHU Feasibility | | | | | | | X |
| Program Sustainability Assessment Tool (PSAT) | | | | | | | X |
| Opioid Roundtables (when stakeholders are available) | X | X | X | X | X | | |
| Implementation Qualitative Interview | | | | | | | X |
| Session Summary Form | | X | X | X | X | | |
| Additional Case Management Form | | | As needed | | | | |
| Work Absenteeism | X | X | X | X | X | | |
| PROMIS Pediatric Anxiety Short Form | X | X | X | X | X | | |

Qualitative: In-depth interviews will use semi-structured theoretically driven interview guides and will be transcribed and thematically coded using emergent coding. From the quantitative data, item frequencies and summary scale scores will be examined to identify barriers and facilitators to program acceptability, feasibility and sustainability.

For the opioid guide, we consulted with other researchers examining substance use in Native American populations to create our semi-structured guide (see Appendix).

5. **Answer the following if they are relevant to your study design:**

A. If the study has different arms, explain the process for assigning participants (intervention/control, case/control), including the sequence and timing of the assignment.

Aim 1: Participants will be stratified by age groups (10-14, 15-19, 20-24, 25-29) and event type (ideation, attempt, binge + recent ideation), then randomized to the control or intervention condition using a 1:1 assignment ratio. Re-randomization of all participants will occur again at CM3 (another 30 days or 60 days/2 months post-baseline assessment).

Aim 3: N/A

B. If human biospecimens (blood, urine, saliva, etc.) will be collected, provide details about who will collect the specimen, the volume (ml) and frequency of collection, how the specimen will be used, stored, identified, and disposed of when the study is over. If specimens will be collected for use in future research (beyond this study), complete the “Biospecimen Repository” section below.

N/A

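### The randomisation strata are stated inconsistently, and the primary SIQ model names no strata terms, no use of baseline SIQ and no rule for combining SIQ with SIQ-JR

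*Combined protocol and SAP*

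**What the plan says.** **Strata.** Five places describe the stratification:

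- Section III.A, Aim 1: "using a blocked randomized design, stratifying participants by age and event type", with no age bands.
- Section V.C.1, opening of the Aim 1 study procedure: "participants will be stratified by gender and event type, and then randomized to New Hope (NH) plus CM, or CM alone".
- Section V.C.1, Randomization Procedure 1: "Participants will be stratified by age groups (10-14, 15-19, and 20-29) and event type".
- Section V.C.1, Randomization Procedure 2: "age groups (10-14, 15-19, and 20-29) and event type (ideation, attempt, binge + recent ideation), then randomized to intervention condition".
- Section V.C.5.A, on assignment to arms: "Participants will be stratified by age groups (10-14, 15-19, 20-24, 25-29) and event type".

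**Model.** Section V.C.4 proposes mixed-effects regression for Aim 1 "to estimate average treatment effects while accounting for shared variance of repeated measures within adolescent" and lists general strengths of such models. It names no fixed effects. Table 2 schedules SIQ/SIQ-JR at all five visits, CM1 to CM5, but section V.C.4 does not say how the CM1 score enters.

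**Outcome.** Section V.C.4 names SIQ/SIQ-JR as a single primary measure. It describes one 15-item scale, and then gives separate thresholds: "Scores of 30 for the SIQ and 23 for the SIQ-JR indicate severe suicidal ideation". The only rule on who receives which form is in section X.C.1 (Safety Monitoring): SIQ from age 15, SIQ-JR below 15.

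**The concern.** The procedure opening and Randomization Procedure 1 describe the same event, yet one stratifies on gender and the other on age. Section V.C.5.A then splits the oldest band in two. Only one scheme can have been built into the randomisation system, and a model that follows the design needs to know which. Stratifying makes the arms more alike on the stratifying factors. If the model leaves out factors that predict SIQ, its standard errors tend to be too wide.

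The baseline score raises a similar question. CM1 SIQ is collected on everyone and may predict later SIQ. If it is not used, precision is lost. If its use is settled after the data are seen, the primary result depends on an analyst's choice.

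The two forms matter because eligible ages run from 10 to 29, so both can occur. The plan's own thresholds differ by form, which means the plan does not treat equal raw scores as equivalent. Without a rule for combining them, the primary outcome is not fully defined.

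**Working it through.** **1. Strata counts.** There are three event types. Two gender levels are assumed.

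| Text | Strata | Cells | Mean per cell (of 304) |
|---|---|---|---|
| V.C.1, procedure opening | gender × event | 2 × 3 = 6 | 50.7 |
| Randomization Procedures 1 and 2 | 3 age bands × event | 3 × 3 = 9 | 33.8 |
| V.C.5.A | 4 age bands × event | 4 × 3 = 12 | 25.3 |

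Section III.A gives no bands, so its cells cannot be counted.

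**2. Reproducing the plan's sample size (section III.B).** The stated inputs are four groups, alpha 0.013, Cohen's f = 0.2, correlation 0.2, 80% power and n = 58 per group. The number of measures m is not stated. I take m = 2, because the four sequences exist only after the CM3 re-randomisation and only CM4 and CM5 follow it.

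Use a between-groups F test with 3 and 4n − 4 degrees of freedom. The noncentrality is λ = f² × 4n / v, where v is the variance of a participant's mean over m visits, in SD² units.

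- v = (1 + (m − 1) × 0.2)/m = 1.2/2 = 0.6
- λ = 0.04 × 232/0.6 = 15.47, so power is 81.3%

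The smallest n for 80% is 57 at alpha 0.013, or 58 at 0.05/4 = 0.0125. The plan's 58 is therefore reproduced with m = 2.

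**3. Adding CM1 SIQ.** Let r be the correlation of CM1 with each of CM4 and CM5. Adjusting for CM1, or constraining the CM1 means to be equal across arms, reduces v to 0.6 − r². The documents do not give r, so a range is shown for n = 58.

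| r (assumed) | v | Variance relative to ignoring CM1 | λ | Power |
|---|---|---|---|---|
| CM1 ignored | 0.60 | 1.000 | 15.47 | 81.3% |
| 0.1 | 0.59 | 0.983 | 15.73 | 82.1% |
| 0.2 | 0.56 | 0.933 | 16.57 | 84.6% |
| 0.3 | 0.51 | 0.850 | 18.20 | 88.6% |
| 0.5 | 0.35 | 0.583 | 26.51 | 98.0% |

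**4. Cost of strata terms that turn out not to predict SIQ.** These only use up error degrees of freedom. With CM1 ignored and n = 58, power goes from 81.25% to 81.23% with 5 terms (6 cells), 81.21% with 8 (9 cells) and 81.19% with 11 (12 cells). The gain when strata do predict SIQ cannot be computed, because the documents give no figure for that association.

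**5. Participants who change form.** If ages are even within 10-14 and form follows age at each visit, the share of under-15s who turn 15 within 180 days is 180/(5 × 365.25) = 9.9%. If ages are even over the 20 years from 10 to 29, under-15s number 304 × 5/20 = 76, and 76 × 0.099 gives about 7 to 8 people. Both age distributions are assumptions.

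**The case against.** Much can be said for the plan. The protocol template asks only for a brief analysis plan, so silence on model terms is missing detail rather than error. Four of the five strata statements agree on age and event type, and both paragraphs headed as randomisation procedures give the same three bands. The gender statement is the outlier and may be a slip. An analyst could fit four age bands, event type and gender and so include every factor named, at negligible cost. Leaving strata out of a linear model tends to be conservative. All of this stands. It limits the weight of the point but does not tell a reader which scheme was used.

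It is also fair that the 0.2 in section III.B need not apply to CM1. If the repeated measures there are CM4 and CM5, the correlation of CM1 with them is not given. This is why step 3 shows a range.

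Three stronger readings are tempting and are not supported:

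- **A severe loss of power from analysing change from CM1.** At r = 0.2 such an analysis would have 42.2% power, but no section plans it. The mention of patterns of change in section V.C.4 belongs to a general list of what mixed models can handle. The figure also moves from 35.0% to 81.3% as r goes from 0.1 to 0.5.
- **Power of 96% or more from four follow-up visits.** The four groups do not exist until after CM3, so only two visits can inform a comparison of all four.
- **Imbalance in form if gender was the stratifier.** Randomisation balances form in expectation under any of the schemes. The age bands, which split at 15, would add balance by stratification. Even they do not guarantee it over the four sequences, because no text stratifies the second randomisation by first assignment.

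**Conclusion.** The point holds as one of reconciliation and specification. The current text gives incompatible strata for one randomisation. The primary model names neither strata terms nor a use of CM1 SIQ, and two forms with different thresholds are treated as one outcome without a combining rule.

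The measurable part is the baseline score. Relative to ignoring CM1, using it properly adds between 0.8 point of power (r = 0.1) and 16.7 points (r = 0.5) at n = 58, and 3.3 points at r = 0.2. This assumes two post-CM3 visits correlated 0.2, the same r with each, and a model that does not already use CM1 in this way. Section V.C.4 is silent; it does not exclude the efficient choice. The gain from strata terms is real only if the strata predict SIQ, and its size is unknown.

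A reader might infer that the trial's result would be biased or its allocation invalid. Nothing here shows that. The form rule is taken from the safety section, so its use for outcome scoring, and any switch at age 15 during follow-up, is itself an inference. The changes are worth making, but they are not a condition for a valid analysis.

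**What to change.** 1. **Strata.** Reconcile section III.A, the three descriptions in V.C.1 and section V.C.5.A to the scheme actually used in the randomisation system. Include those strata as fixed effects in the primary SIQ model.
2. **Baseline.** Use CM1 SIQ once: either as a covariate, with CM1 removed from the outcome vector, or as an outcome with means constrained equal across arms at baseline. Do not adjust for CM3 SIQ in contrasts that include New Hope. CM3 is measured after New Hope, so adjustment could remove part of its effect.
3. **Forms.** Do not pool raw SIQ and SIQ-JR scores without either a form term or standardisation within form. Report raw points alongside, so that results can be read against the 25% reduction in section III.B. Add a sensitivity analysis for participants who change form.

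The cost is analysis-plan wording and a few model terms from data already collected, with no new visits or instruments. No change is proposed to which form is given or to the risk cut-offs.

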After 30 days from CM3, all youth will be visited by Research Program Assistants and complete a fourth assessment (CM4). The 30-day time frame between CM3 and CM4 will allow ample time to complete the ER intervention with participants and assess any changes in resilience across study groups. To track long-term outcomes, all youth will complete a final assessment 3 month later (CM5: 6 months post-enrollment). All youth will be followed to the end of the study period (up to 4.75 years from the first participant’s enrollment) for any subsequent suicide events using the Apache surveillance system. If necessary, assessments may be conducted over the phone for participants who start in the study but are located elsewhere during an assessment timepoint.

As part of the economic evaluation supplement, our staff will be asked to fill out time logs listing how they spent time the preceding day. This will not affect the study participants in any way.

Aim 3: STUDY PROCEDURE

If stakeholders provide informed consent, they will be interviewed by Drs. [name] or [name] using a semi-structured guide to gather their views on the Southwest Hub’s key intervention components (Surveillance/Case Management, New Hope and Elders’ Resilience Interventions). They will also be asked to participate in a 2x annually administered online survey to better understand how capacity for sustainability changes over time. If they consent to the online survey, the Program Sustainability Assessment Tool (PSAT) will be administered via email to participants every six months.

2. Describe the number and type of study visits and/or contacts between the study team and the participant, how long they will last, and where/how they will take place.

Aim 1: Five study visits will take place over the course of 6 months. All study visits will take place in the participants' home or a private location.

CM1: Recruitment, consent, randomization, baseline assessment: 2 hours

Intervention Group: NH: 2-4 hours

CM2: Assessment: 1 hour

CM3: Assessment and randomization: 1 hour

Intervention Group: EC: 2-4 hours

CM4: Assessment: 1 hour

CM5: Assessment: 1 hour

Opioid Data Collection Sub-Study (for a subset): Additional 60-90 minutes interview

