As is standard practice, CMHVs will refer all youth to care outside of the study, including referrals to mental health care providers, traditional healers, and spiritual leaders. In addition, we have an established protocol created as part of previous studies to ensure triage and access to emergency care for youth who are at immediate risk for suicide. This procedure was approved by Tribal, Hopkins and IHS IRBs, and will be employed by CMHW for this project. At the close of each visit, youth will complete the Suicide Ideation Questionnaire (SIQ/SIQ-JR) and Opioid Risk Tool. CMHVs immediately score SIQ and Opioid Risk Tool at the time of visit, and depending on score will respond in a graduated fashion. Youth may also be viewed as higher risk if a staff member working with them has concerns.

VI. Data Security and Confidentiality Protections:

A. Personally Identifiable Information (PII):

Please identify the Personally Identifiable Information (PII) that you may be collecting and using at any of the following stages of your study: ***Recruitment, Consent, and Study Implementation.***

| | |
|-------------------------------------------------------------------------------------------------------------------------------------------------------|-------------------------------------|
| Name, signature, initials, or other identifiable code |  |
| Geographic identifier: address, GPS location, etc. |  |
| Dates: birth, death, clinical service, discharge, etc. |  |
| Contact information: phone numbers, email address, etc. |  |
| ID: Social Security Number, driver's license number, etc. |  |
| Health record identifiers: medical record, insurance plan number, etc. |  |
| Account numbers |  |
| Device identifiers: e.g., implants |  |
| Internet identifiers: IP address, social media accounts |  |
| Biometric identifiers, including finger and voice prints |  |
| Audio recordings |  |
| Video or full face photographic images |  |
| Genomic/genetic data |  |

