Aim 1: The PIs assume responsibility for the safety of study participants. Research Program staff will be trained to monitor for safety of study participants and report any concerns immediately to the Local Project Director, the Clinical Research Supervisor and the PIs. All Research Program staff will be trained in human subject's research and will be required to complete the CITI ethics module prior to any interaction with participants or study data. Certificates of human subject's completion will be kept on file at the Center for American Indian Health's office in Baltimore.

To determine and quantify the participant's current risk for suicide at the close of all study visits, the Research Program Assistants will complete the Suicide Ideation Questionnaire (SIQ) (participants 15 and over) or the SIQ-JR (participants <15years) with participants. The screen will identify recent suicidal ideation

or behavior, worsening of psychopathology and recent acute stressors. Research Program Assistants will immediately score the SIQ. Depending on the SIQ score, the Research Program Assistants will administer the SIQ-Past Few Days, and then respond in a graduated fashion based on the following risk categories as determined by the SIQ /SIQ-Past Few Days: 1) Does not Appear at Risk; 2) At Some Risk; 3) At Medium to Very High Risk. The following actions, which are clearly outlined in the consent form and will be reviewed prior to each assessment, are taken depending on the SIQ/SIQ-Past Few Days Risk Score:

If the SIQ score is below 37 or SIQ-JR is below 16, the risk category is deemed to be **“Does Not Appear at Risk.”** Research Program Assistant takes the following steps:

When the SIQ does not identify any acute risks and Research Program Assistant observations corroborate this impression, no additional immediate action is needed. If staff has any concerns about these participants, they should not hesitate to contact:

- Local Project Director, [name], Whiteriver, AZ
- Principal Investigators, [name], PhD and [name], PhD, Baltimore, MD
- Clinical Research Supervisor, [name] [name], PhD, Baltimore, MD

If the SIQ score is 37 or above, the SIQ-Jr is 16 or above, and 0 items on the SIQ-Past Few Days scored a 4, 5, or 6 the risk category is deemed to be **“At some risk”**.

Research Program Assistants take the following steps:

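### The protocol gives conflicting orders for baseline assessment and randomisation at CM1, and its close-of-visit SIQ rule leaves open a primary-outcome baseline answered after allocation

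*Combined protocol and SAP*

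**What the plan says.** **Order at CM1.** Section III.A has youth complete the baseline and then says "During the same visit, youth will be randomized 1:1 to either New Hope (NH) plus Case Management (CM), or CM alone". Section V.C.1 has staff administer the baseline assessment; its next sentence says that in the same visit "participants will be stratified by gender and event type, and then randomized to New Hope (NH) plus CM, or CM alone". The visit list in V.C.2 gives the other order: "CM1: Recruitment, consent, randomization, baseline assessment: 2 hours".

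**Order at CM3.** Sections III.A and V.C.1 both say that, after a further 30 days, "all participants will be re-assessed and re-randomized". The visit list agrees: "CM3: Assessment and randomization: 1 hour".

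**Timing of the SIQ.** Section V.C.5.F.f (referral to outside care) says "At the close of each visit, youth will complete the Suicide Ideation Questionnaire (SIQ/SIQ-JR) and Opioid Risk Tool". Section VII.C, under worsening of symptoms, says "At the close of each visit, youth will complete the Suicide Ideation Questionnaire (SIQ/SIQ-JR"). Section X.C.1 has staff complete the SIQ or SIQ-JR to determine "risk for suicide at the close of all study visits".

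**Role of the SIQ.** Section V.C.4 names the SIQ/SIQ-JR as the primary outcome measure. Table 2 has one SIQ row, marked once at each of CM1 to CM5. The SIQ-Past Few Days in VII.C and X.C.1 is a follow-up for those who score above a cutoff, not a second SIQ.

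**The concern.** A baseline value earns its place in a randomised comparison because the allocation cannot have influenced it. The SIQ is self-reported, and a participant offered a New Hope session of 2 to 4 hours will know it. If the SIQ is answered after that offer, relief or disappointment could move the starting score differently in the two arms. Any analysis that uses the score as a starting point would carry part or all of that difference into the treatment effect. The same applies at CM3 if the score there serves as the value before Elders' Resilience.

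Staff who follow the CM1 line of the visit list, or the close-of-visit rule, could produce such a baseline while complying with the protocol. Different staff could also follow different passages, so the order could vary between participants without any record of it.

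**Working it through.** The question is one of sequence, and the plan gives no figure to reproduce. The check sets the passages side by side.

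| Visit | Source | Order given |
|---|---|---|
| CM1 | III.A | baseline, then randomisation |
| CM1 | V.C.1 | baseline, then randomisation |
| CM1 | V.C.2 visit list | randomisation listed before baseline |
| CM3 | III.A and V.C.1 | assessment, then re-randomisation |
| CM3 | V.C.2 visit list | assessment listed before randomisation |
| Every visit | V.C.5.F.f, VII.C, X.C.1 | SIQ at the close |

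1. *CM1.* Two procedural passages agree with each other and the visit list differs. In the V.C.1 quotation, the word then orders stratification before randomisation. The assessment-first order comes from the sentence before it, which has the baseline assessment administered.

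2. *The close-of-visit rule.* Randomisation is inside CM1 and CM3. A questionnaire completed at the close of those visits would normally come after it. None of the three safety passages exempts CM1 or CM3.

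3. *Whether a second SIQ could resolve this.* Table 2 schedules one SIQ per visit, and no passage describes a safety SIQ distinct from the outcome SIQ. As written, the closing SIQ and the outcome SIQ appear to be the same administration, so V.C.1 does not settle when the SIQ itself is answered.

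4. *CM3.* The visit list, III.A and V.C.1 all put assessment first. The possibility of a post-allocation SIQ there rests on the close-of-visit wording alone.

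5. *Safeguards.* V.C.1 requires the SIQ to be scored before staff leave the youth, but gives no order relative to randomisation. V.C.5.F.a answers yes to staff blinding and gives no mechanism. No passage says when allocation is disclosed to the participant.

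**How a shift would carry through (illustration only).** Let d be the between-arm difference in baseline SIQ caused by knowing the allocation, and t the true effect at follow-up. A change-from-baseline contrast estimates t − d, so the full shift enters. A baseline-adjusted contrast estimates t − r × d, where r is the baseline-to-follow-up correlation (equal variances assumed). With r = 0.2, the planning correlation in III.B, each point of d moves the adjusted estimate by 0.2 × 1 = 0.2 points, against 1 point for the change score. The documents give no value for d. Section V.C.4 specifies mixed-effects models without saying how baseline enters, so which contrast applies is also open.

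**The case against.** The best defence is that III.A and V.C.1 describe procedure and agree, while the V.C.2 line answers a form question about number, type and length of visits. It may be a list of contents, not a sequence. That is fair. However, recruitment and consent stand in time order in that line, and the CM3 line in the same list puts assessment before randomisation, so staff could reasonably read the order as meaningful.

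A second defence is that the close-of-visit passages concern triage and never mention randomisation. Section VII.C elsewhere places the SIQ within the first assessment visit, and V.C.1 asks only that it be scored before staff leave. Both fit an SIQ late in the battery with allocation after it. This shows that a sound order is compatible with the text, not that the text requires one.

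A third is that the SIQ covers the past six months, so news of an assignment minutes earlier may move it little. This stands and limits the likely size.

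A reader might infer that the protocol schedules the SIQ after participants have been told their allocation, at both visits. The documents do not support that. Disclosure timing is not stated, and at CM3 the visit list and procedure text both put assessment first. Nor do they support a figure for the bias: no shift is documented, and neither a change-score nor a baseline-covariate analysis is specified.

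**Conclusion.** The point holds as an internal inconsistency with a possible effect on the primary outcome. At CM1 the visit list contradicts III.A and V.C.1. The close-of-visit rule would also normally place the SIQ after randomisation at CM1 and, by that wording alone, at CM3. The baseline SIQ and the pre-Elders' Resilience SIQ may therefore be answered with allocation known.

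The conclusion rests on two inferences: that a closing questionnaire follows a randomisation made within the same visit, and that the closing SIQ is the one scheduled in Table 2. The size of any bias is unknown and may be small. It should still be corrected, since it touches the primary outcome and the remedy is cheap.

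**What to change.** - In V.C.2, reorder the CM1 line to consent, baseline assessment, randomisation.
- In V.C.1 and X.C.1, state that at CM1 and CM3 the outcome SIQ/SIQ-JR and the rest of the battery are completed and submitted before allocation is generated or revealed, and that this score is the pre-randomisation value used in the analysis.
- The investigators must reconcile V.C.5.F.f, VII.C and X.C.1 on the timing of the closing safety SIQ and say whether it is the same administration as the outcome SIQ. If it is separate, record it separately and do not use it as the baseline.
- For participants already enrolled, check and report the order actually followed, from form timestamps if they exist.

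The cost is protocol wording and a check on form order. If a separate closing SIQ is kept, participants may have a short repeat questionnaire at CM1 and CM3; V.C.4 describes the SIQ as 15 items. The documents do not describe the randomisation system, so the means of enforcing the order is left to the study team.
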